1. SYNOPSIS

[figure not shown]
Name of Sponsor/Company: Sage Therapeutics, Inc. (hereafter referred to as Sage Therapeutics, or Sage)	
Name of Investigational Product: SAGE-718 oral softgel lipid capsule	
Name of Active Ingredient: SAGE-718	
Protocol Number: 718-CNP-202	
IND Number: 134217	
EudraCT Number: not assigned	
Title of Study: A Randomized, Double-blind, Placebo-controlled Study to Evaluate the Effects of SAGE-718 in Parkinson's Disease Cognitive Impairment	
Short Title: A Study to Evaluate the Effects of SAGE-718 in Participants with Parkinson's Disease Cognitive Impairment	
Number of Sites and Study Location: Approximately 30 sites in the United States	
Phase of Development: 2	
Planned Duration for each Study Participant: The duration of participation (from Screening through the final Follow-up visit) for each participant is estimated to be up to 14 weeks, including 3-week Screening Period, 1-week Baseline Period, 6-week Treatment Period, and 4-week Follow-up Period.	
Objectives and Endpoints:	
Objectives	Endpoints
Primary	

To evaluate the effect of SAGE-718 on cognitive performance in participants with Parkinson's Disease (PD)-Mild Cognitive Impairment (MCI).	
Change from Baseline to Day 42 in the Wechsler Adult Intelligence Scale-IV (WAIS-IV) Coding test.
Secondary	

To evaluate the safety and tolerability of SAGE-718 in participants with PD-MCI.	
Proportion of participants experiencing treatment -emergent adverse events (TEAEs) and severity of TEAEs.Number of participants who withdraw due to adverse events (AEs).
■■■■■	

To evaluate the safety and tolerability of SAGE-718 on other safety parameters.	
Change from Baseline in vital signs, clinical laboratory parameters, electrocardiograms (ECGs), and ■■■■■

Study Description:

This is a randomized, placebo-controlled, double-blind study to evaluate the effects of SAGE-718 in PD cognitive impairment.

Eligible participants with a confirmed diagnosis of idiopathic PD by 2015 Movement Disorder Society (MDS) criteria at Screening and who meet MDS Task Force Criteria for MCI in PD (excluding requirement for United Kingdom (UK) PD Brain Bank diagnostic criteria) will receive a 1.2 mg dose of SAGE-718 or placebo daily for 6 weeks.

Assessments will be performed as outlined in the Schedule of Assessments ([Table 2](#)) and the Schedule of [REDACTED], Biochemical and Genetic Sampling ([Table 3](#)). The scales are to be administered after the daily dose of investigational product (IP) during the Treatment Period, and at approximately the same time of day (± 2 hours) throughout the study. For participants receiving medication for PD symptoms, assessments are to be administered in the “on” state (defined as the period in which motor symptoms are mitigated due to the effects of PD medication).

Abbreviations: Cognition = Cognitive assessments (includes Wechsler Adult Intelligence Scale-IV [WAIS-IV] Coding test; [REDACTED], and Montreal Cognitive Assessment [MoCA]. [REDACTED]

[REDACTED]; PD-MCI = Parkinson's Disease Mild Cognitive Impairment; [REDACTED]; PO = orally.

See [Table 2](#) for specific schedule of each test.

Screening Period

The Screening Period begins with the informed consent process for prospective participants, including optional caregivers. Subsequent screening assessments will be performed between Day -28 and Day -8 to determine eligibility, including assessments of cognitive and motor function. An adult caregiver is optional but highly recommended for each participant to support completion of study activities and to answer questions about the participant's condition.

Baseline Period

The Baseline Period will occur from Day -7 through Day -1. On Day -7, participants will visit the clinic for confirmation of continued eligibility and collection of baseline cognitive and safety data. Participants and caregivers will receive training on the study procedures and devices. Participants will continue to complete daily assessments of cognitive symptoms using the mobile device during the Baseline Period.

Treatment Period

Eligible participants will be randomized 1:1 to receive 1.2 mg of SAGE-718, or matching placebo for 42 days. Beginning on Day 1 and continuing through Day 42, participants will self-administer blinded investigational product (IP) once per day in the morning. No dosing will be permitted beyond Day 42.

At scheduled clinic visits during the Treatment Period, safety, efficacy, and [REDACTED] will be performed, and study staff will dispense a sufficient amount of IP for daily administration until the next scheduled study visit. Adherence to the dosing regimen will be assessed at each in-clinic visit by examination of the used packaging and counting any returned capsules.

During the Treatment Period, participants will be able to receive IP if there are no dose limiting safety/tolerability concerns. Participants who discontinue IP early should complete the remaining study visits as scheduled unless the participant withdraws consent or loses the capacity to grant consent. If a participant withdraws from the study/stops study participation early, an early termination visit should be conducted. Treatment with SAGE-718 can be ended without down titration.

Follow-up Period

After completing the treatment period, participants will return to the clinic for follow-up visits on Day 70 to collect continued safety, efficacy, and [REDACTED].

Number of Participants (planned): Up to 76 participants will be dosed to obtain up to 30 evaluable participants per treatment arm.

Eligibility Criteria

Inclusion Criteria:

Each eligible participant must:

1. be capable of providing informed consent;
2. have signed an informed consent form (ICF) prior to any study-specific procedures being performed;
3. be willing and, in the opinion of the investigator, able to comply with study procedures;
4. be between the ages of 50 and 75 years, inclusive, at Screening;
5. meet the following criteria for PD-MCI:
 - a. have a confirmed diagnosis of idiopathic PD according to 2015 MDS clinical diagnostic criteria, and
 - b. meet MDS Task Force Criteria for MCI in PD (excluding requirement for UK PD Brain Bank diagnostic criteria).
6. meet the following criteria for MoCA:
 - a. for participants meeting Level 1 PD-MCI criteria, have a MoCA score of 20 to 25 (inclusive) at Screening;
 - b. for participants meeting Level 2 PD-MCI criteria (within the past year), have a MoCA score of 18 to 25 (inclusive) at Screening;
7. be able to complete the Color Trails Test 1 (including the ability to follow rater redirection and correct errors), and, based on participant's performance and investigator's opinion, is expected to be capable of engaging in prolonged cognitive testing for the duration of the study.
8. meet criteria for modified Hoehn and Yahr Stage I to III (mild to moderate motor severity) at Screening;
9. have stable motor symptoms for at least 4 weeks prior to Screening, in the opinion of the investigator;
10. have stable concomitant medication dose and frequency for at least 4 weeks prior to the first IP administration, and which is expected to remain stable for the duration of the study;
11. agree, if female, to use an acceptable highly effective method of contraception during participation in the study and for 30 days following the last dose of IP (refer to Section 8.2.4 for acceptable forms of contraception), unless they are postmenopausal (defined as no menses for 12 months without an alternative medical cause and confirmed by follicle stimulating

hormone [FSH] >40 mIU/mL), surgically sterile (hysterectomy or bilateral oophorectomy or bilateral salpingectomy), or does not engage in sexual relations which carry a risk of pregnancy (does not include abstinence);

12. agree, if male, to use an acceptable method of highly effective contraception during the Treatment Period and for 30 days after receiving the last dose of IP, unless the participant does not engage in sexual relations that carry a risk of pregnancy (refer to Section 8.2.4 for acceptable forms of contraception);
13. agree, if male, to abstain from sperm donation during the Treatment Period and for 30 days after receiving the last dose of IP and
14. agree to refrain from drugs of abuse for the duration of the study and from alcohol during the 48 hours preceding each study visit.

Exclusion Criteria

Each eligible participant must not:

1. have participated in a previous clinical study of SAGE-718, have participated in a previous gene therapy study, or have received study treatment in any other drug, biologic, or device trial within 30 days or 5 half-lives (whichever is longer), unless the participant participated solely in the placebo arm of the study;
2. have clinically significant comorbid medical conditions, a chronic condition that is unstable, or are taking concomitant medications that, in the opinion of the investigator, may make the participant unsuitable for inclusion or have the potential to compromise safety and/or compliance with study requirements;
3. have a diagnosis of dementia of any etiology, including but not limited to: Dementia with Lewy Bodies, Alzheimer's Dementia, and Vascular Dementia;
4. have any parkinsonism other than PD, including secondary parkinsonism or atypical parkinsonism;
5. be experiencing motor symptoms or fluctuations in motor symptoms associated with PD that will interfere with completing study procedures, including assessments administered by touch-screen devices, in the opinion of the investigator;
6. have an ongoing central nervous system condition other than PD that in the opinion of the investigator could influence the outcome of the study (including active neurologic and/or nonremitting psychiatric disorders);
7. have experienced significant psychotic symptoms, including hallucinations or delusions, within the past 3 months, in the opinion of the investigator;
8. have a history of brain surgery, deep brain stimulation, or any history of hospitalization due to a brain injury;
9. have a history, presence, and/or current evidence of clinically relevant intracranial abnormality (eg, stroke, hemorrhage, space-occupying lesion);
10. be receiving any of the following prohibited medications:
 - a. medications with potent effects at the N-methyl-D-aspartate (NMDA) receptor, including memantine^a, amantadine, ketamine, or related compounds.
 - b. medications that inhibit cholesterol absorption (eg, ezetimibe).
 - c. bile acid sequestrants (eg, colestevam, cholestyramine).
 - d. other medications given at doses, frequencies, or in combinations that are likely, in the opinion of the investigator, to have a deleterious effect on cognitive performance.

- e. cannabis or other tetrahydrocannabinol (THC)-containing substances (any route of administration), regardless of whether or not they are prescribed.

^aMemantine is prohibited within 30 days of screening and during the entire course of the study.

- 11. have an alcohol or drug use disorder within the past 12 months as per Diagnostic and Statistical Manual of Mental Disorders (DSM-5) criteria;
- 12. have a history of seizures or epilepsy, with the exception of a single episode of febrile seizures in childhood;

[REDACTED]

- [REDACTED]
- [REDACTED]
- [REDACTED]
- [REDACTED]
- [REDACTED]
- [REDACTED]
- [REDACTED]

- 14. have any of the following clinically significant medical conditions:
 - a. any clinically significant finding on 12-lead ECG during Screening or Baseline
 - b. any clinically significant supine vital signs (heart rate, systolic and diastolic blood pressure) during Screening or Baseline (note: vital sign measurements may be repeated once).
- 15. have significant hepatic, renal, cardiovascular, pulmonary, gastrointestinal, hematological, immunologic, ophthalmologic, metabolic, or oncological disease;
- 16. have a history, presence, and/or current evidence of serologic positive results for human immunodeficiency virus (HIV)-1 or HIV-2, and/or has detectable hepatitis B surface antigen, anti-hepatitis C virus (HCV) or positive HCV viral load at Screening;
- 17. have a positive pregnancy test, be pregnant, be lactating, or intend to breastfeed during the study;
- 18. be investigative site personnel, sponsor personnel, or an immediate member of their family (spouse, parent, child, or sibling whether biological or legally adopted); or
- 19. is known to be allergic to any SAGE-718 excipients, including soy lecithin.

Investigational Product Dosage and Mode of Administration:

SAGE-718 1.2 mg or matching placebo will be self-administered as oral softgel lipid capsule(s) once daily in the morning.

Duration of Treatment: IP will be administered once daily for 42 days (6 weeks).

Statistical Methods:

A separate statistical analysis plan (SAP) will provide a detailed description of the analyses to be performed in the study. The SAP will be finalized and approved prior to database lock.

General Considerations

Unless otherwise specified, Baseline is defined as the last measurement prior to the first dose of IP. Continuous endpoints will be summarized with n, mean, standard deviation, median, minimum and maximum, Q1, and Q3. In addition, change from baseline values will be calculated at each time point and will be summarized using the same summary statistics. Out of range safety endpoints may be

categorized as low or high, where applicable. For all categorical endpoints, summaries will include counts and percentages.

Analysis Sets

The All Randomized Set will include all participants who have been randomized and will be used to describe participant disposition.

The Safety Set will include all participants who were administered at least one dose of the IP and will be used to describe the safety data.

The Full Analysis Set will include all participants in the Safety Set who have baseline and at least 1 postbaseline efficacy evaluation.

Safety Analysis

AEs will be coded using the Medical Dictionary for Regulatory Activities (MedDRA) version 22.0 or higher. A TEAE is defined as an AE with onset after the first dose of IP. The proportion of participants experiencing TEAEs will be displayed by treatment group and by system organ class and preferred term. In addition, summaries will be provided by intensity (mild, moderate, severe) and by causality (related, not related) to IP. Any TEAEs leading to discontinuation or interruption of treatment or withdrawal from the study and any treatment-emergent SAEs will be summarized. All AEs and SAEs (including those with onset or worsening before the start of IP) through the end of the study will be listed. Vital signs, laboratory parameters, ECGs, [REDACTED] data will be summarized by treatment group. Additional analyses will be detailed in the SAP.

Efficacy Analysis

The endpoints for each cognitive test, including individual scores for the WAIS-IV Coding test [REDACTED]

[REDACTED] Descriptive statistics of scores and change from baseline scores will be summarized based on the Full Analysis Set. These endpoints will also be analyzed using a mixed effects model for repeated measures. The model will include change from baseline scores as dependent variable; treatment, visit, and visit by treatment interaction as fixed effects; participants as random effects; and baseline cognitive test scores as a covariate. Model-based point estimates (ie, least square means, their 95% confidence intervals, and associated p values) at each time point (visit) will be reported where applicable. Line plots of change from baseline scores will be plotted with standard error bars. [REDACTED]

[REDACTED] will be analyzed using similar methods.

Sample Size Calculation

Assuming a placebo-adjusted treatment effect size of 0.75 (Burdick 2014) in the WAIS-IV Coding test, a total sample size of 60 evaluable participants (30 per arm) will provide 80% power at a two-sided significance level $\alpha=0.05$.

Adjusting for an anticipated 20% dropout rate, approximately 76 participants will be randomly assigned in a 1:1 ratio to either SAGE-718 or placebo.

Table 2: Schedule of Assessments

Assessments ^a	Screening Period	Baseline	Treatment Period				Follow-Up Period
	Days -28 to -8	Day -7 (±2 days)	Day 1 ^b	Day 14 (±2 days)	Day 28 ^c (±2 days) Phone Call	Day 42 ^d (-2 days)	Day 70 (±4 days) or ET
Informed consent ^e	X						
Inclusion/exclusion criteria	X	X	X				
Randomization				X			
Medical history and demographics ^f	X						
Participant training ^g	X	X					
Body weight	X		X			X	X
Body height	X						
Vital signs (including orthostatics) ^h	X		X	X		X	X
Physical examination ⁱ	X		X	X		X	X
FSH test ^j	X						
Serology test ^k	X						
12-lead ECG ^l	X			X		X	X
Clinical laboratory assessments ^m	X		X	X		X	X
Urine drug test	X		X	X		X	X
Alcohol breath test	X		X	X		X	X
Pregnancy test ⁿ	X		X				X
Optional biochemical research sample ^o	X			X		X	
Optional genetic research sample ^o	X						

Assessments ^a	Screening Period	Baseline	Treatment Period				Follow-Up Period
	Days -28 to -8	Day -7 (±2 days)	Day 1 ^b	Day 14 (±2 days)	Day 28 ^c (±2 days) Phone Call	Day 42 ^d (-2 days)	Day 70 (±4 days) or ET
Modified Hoehn and Yahr stage scale	X						
WAIS-IV Coding Test		X	X	X		X	X
[REDACTED] and PDAQ-15 Knowledgeable Informant) ^r		X				X	X

Assessments ^a	Screening Period	Baseline	Treatment Period				Follow-Up Period
	Days -28 to -8	Day -7 (± 2 days)	Day 1 ^b	Day 14 (± 2 days)	Day 28 ^c (± 2 days) Phone Call	Day 42 ^d (-2 days)	Day 70 (± 4 days) or ET
Daily mobile assessment ^t (DSST, PVT, sleep diary)					X		
IP self-administration ^u				X (once daily in the morning)			
IP dispensation ^v			X	X			
IP accountability/return ^w			X	X		X	
AEs/SAEs ^x	X	X	X	X	X	X	X
Prior and concomitant medications ^y				X			

Abbreviations: AE = adverse event, [REDACTED] COVID-19 = coronavirus disease 2019;

[REDACTED] DSST = Digit Symbol Substitution Test; ECG = electrocardiogram; ET = early termination; FSH = follicle-stimulating hormone; HIV = human immunodeficiency virus; ICF = informed consent form; IP = investigational product; [REDACTED]

[REDACTED] PD = Parkinson's Disease; [REDACTED] PDAQ-15 KI = Penn Parkinson's Disease Activities Questionnaire-15 Knowledgeable Informant; [REDACTED] PRO = patient-reported outcome; PVT = Psychomotor Vigilance Task; SAE = serious adverse event; [REDACTED] WAIS-IV = Wechsler Adult Intelligence Scale-IV.

^a The scales are to be administered after the daily dose of IP during the Treatment Period, and at approximately the same time of day (± 2 hours) throughout the study. For participants receiving medication for PD symptoms, the scales are to be administered in the “on” state (defined as the period in which motor symptoms are mitigated due to the effects of PD medication). For clinician administered scales, the same individual should administer the scale whenever possible.

^b All tests on Day 1 will be conducted predose.

^c Phone check-in only for AEs/SAEs and changes to medical history or medications.

^d Dosing ends on Day 42.

^e Both participants and caregivers (if applicable) will be consented during the Screening Period.

^f In addition to full medical history, including family history of PD, all medications and supplements taken within 60 days prior to Screening, all medications used to treat PD regardless of timing, and all nonpharmacological methods (eg, psychosocial, psychotherapeutic) used to treat or prevent [REDACTED] [REDACTED], and cognitive manifestations of PD are to be recorded. Information regarding diagnosis, isolation, and/or hospitalization due to COVID-19 will be documented as part of medical history, AE collection, and prior/concomitant medication/procedure collection at Screening and throughout the study.

^g Participants and caregivers (if applicable) will be trained by study staff on the use of software applications and devices necessary for the conduct of the study.

^h Vital signs include body temperature, respiratory rate, heart rate, and blood pressure. Vital signs will be measured prior to dosing on days when IP is administered. Blood pressure and heart rate will be measured after the participant has been in the supine position for at least 5 minutes and then repeated approximately 1 and 3 minutes after standing, at all scheduled time points.

ⁱ A full physical examination will be conducted during Screening and at Day 42 (End of Treatment). At other visits, an abbreviated physical examination will include a brief assessment of general appearance, cardiovascular, respiratory, gastrointestinal, and neurological systems, followed by a targeted physical assessment as needed. A symptom directed examination may be conducted at any time at the discretion of the investigator.

^j Serum FSH test will be conducted at Screening for the female participants who are not surgically sterile to confirm whether female participants with ≥12 months of spontaneous amenorrhea meet the protocol-defined criteria for being postmenopausal.

^k To include hepatitis B and C screening tests, HIV-1 and -2 antibody.

^l A single ECG will be measured after the participant has been in the supine position for at least 5 minutes.

^m Clinical laboratory assessments will include blood samples for hematology, biochemistry, coagulation, and urine samples for urinalysis. Samples will be collected prior to dosing on days when IP is administered. On nondosing days, collection may occur at any time.

ⁿ Serum pregnancy tests will be conducted for all female participants at Screening; urine pregnancy tests will be conducted at other scheduled time points for female participants who are not postmenopausal or surgically sterile.

^o Refer to [Table 3](#) for details.

[REDACTED]

[REDACTED]

[REDACTED]

[REDACTED]

^r PDAQ-15 Knowledgeable Informant is provided by caregiver.

[REDACTED]

^t Daily reminders will be sent to participants via a mobile device to complete assessments on remote device. Daily assessments include the [REDACTED] DSST, PVT, and the National Sleep Foundation Sleep Diary. It is recommended that assessments are completed at approximately the same time each day, within 1 hour following IP administration. Daily mobile assessments should be completed in a quiet area of participant's home. On dosing days the remote assessment will be completed in the clinic following dosing under observation by the study staff.

^u On Days 1, 14, and 42, the participants will self-administer IP in the clinic under the supervision of study staff. All scheduled safety assessments will be conducted prior to dosing and all scheduled cognitive tests will be administered postdosing.

^v Study staff will dispense enough IP for the participant to take daily at home until the next scheduled visit.

^w Participants will bring all used packaging and unused IP to the clinic at each visit for study staff to review and document.

^x AEs/SAEs collected from time of ICF throughout the duration of participation.

^y At Screening, to include all medications and supplements taken within 60 days and all medications used to treat PD regardless of timing. At subsequent visits, all changes to any medication should be captured.

Table 3: Schedule of [REDACTED], Biochemical, and Genetic Sampling

Assessments	Screening	Baseline	Treatment		Follow-Up	
	Days -28 to -8	Day -7 (± 2 days)	Day 1	Day 14 (± 2 days)	Day 42 (-2 days)	Day 70 (± 4 days) or ET
[REDACTED]						
Predose				X	X	X
Optional blood collection: biochemical research ^b						
	X			X	X	
Optional blood collection: genetic research						
	X					

Abbreviations: ET = early termination; IP = investigational product; [REDACTED]

^b Biochemical samples will be collected at any time during Screening. On Days 14 and 42, the samples will be collected at times corresponding with the [REDACTED] blood draw.

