8.4. Treatment Adherence

Beginning on Day 1 and continuing through Day 42, participants will self-administer blinded IP once per day in the morning. At clinic visits, participants will self-administer the IP under staff supervision, followed by assessments of cognitive function, [REDACTED]

[REDACTED]. Study staff will dispense sufficient IP for daily administration until the next scheduled study visit. Adherence to the dosing regimen will be assessed at each in-clinic visit by examination of the used packaging, and counting any returned capsules. This information will be documented in the source files and interactive response technology (IRT), along with any deviations from the prescribed dosage regimen. Details about IP accountability are included in Section [9.6.1](#).

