10. SCREENING, EFFICACY AND CLINICAL PHARMACOLOGY ASSESSMENTS

A variety of measures will be employed in this study to evaluate cognitive function, [REDACTED]. All assessments are to be completed according to the Schedule of Assessments ([Table 2](#)) and the Schedule of [REDACTED], Biochemical and Genetic Sampling ([Table 3](#)).

During the Screening and Baseline Period, participants will be trained by study staff on the use of all software applications and devices necessary for the conduct of the study.

These assessments are to be administered after the daily dose of IP during the Treatment Period, and at approximately the same time of day (± 2 hours) throughout the study. For participants receiving medication for PD symptoms, assessments are to be administered in the “on” state (defined as the period in which motor symptoms are mitigated due to the effects of PD medication). For clinician administered scales, the same individual should administer the scale whenever possible.

In-clinic visits will entail cognitive assessment administered by computer-based and paper/pen forms, self-report questionnaires, and interview measures.

Participants will complete daily assessments each morning during the Treatment Period. Participants will also be issued a mobile device that will be used to complete daily assessments. At scheduled clinic visits, the task will be performed in the clinic under observation by study staff, otherwise the participant will perform this task remotely (at home).

An adult caregiver is optional but highly recommended for each participant to support completion of study activities and to answer questions about the participant’s condition.

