Every attempt will be made to avoid missing data. All participants will be used in the analyses, as per the analysis populations, using all non-missing data available. No imputation process will be used to estimate missing data unless otherwise specified.

General definitions are defined as below:

- Baseline is defined as the last non-missing measurement prior to the first dose of IP, unless stated otherwise. If the time of an assessment is collected, baseline will be the latest assessment prior to first dose of IP administration time; if the time of an assessment is not collected, the assessment on Day 1 is assumed to be prior to dosing

if the protocol mentions that this assessment needs to be before dosing or it is collected as "pre-dose".

- Study day 1 is defined as the date of randomization for untreated randomized participants or the date of first dose for treated participants.
- Study day will be calculated relative to the date of randomization for untreated randomized participants and relative to the date of first dose for treated participants.
 - If event is prior to randomization or the first dose, then study day is calculated as:
Date of Event – Date of Randomization or First Dose
 - If event is after randomization or the first dose, then study day is calculated as:
Date of Event – Date of Randomization or First Dose + 1

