8.3.1. Definition of Efficacy Variables

8.3.1.1. Primary Efficacy Assessment

The WAIS-IV Coding test is a valid and sensitive measure of cognitive dysfunction impacted by many domains that correlates with real-world functional outcomes (e.g., the ability to accomplish everyday tasks) and recovery from functional disability. In-clinic administration of the WAIS-IV Coding test will use the traditional paper-and-pen format, in which the participant is required to identify the symbols matched to numbers using a key and write in the symbol beneath the associated number. The score is based on the total number of codes correctly completed over a 120 second time limit (higher scores reflecting better performance).

WAIS-IV Coding Test is collected at Baseline (Day -7), Day 1 (pre-dose), Day 14, Day 42 and Day 70.

[REDACTED]

A series of horizontal black bars of varying lengths, with a few small vertical black marks on the left side.

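### Footnotes b and u set opposite times for the Day 1 WAIS-IV Coding test, and the SAP's default for untimed scores can accept a postdose score as the primary baseline

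*Protocol*

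**What the plan says.** Protocol Table 2 schedules WAIS-IV Coding on Day -7, Day 1, Day 14, Day 42 and Day 70.

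- Footnote b, attached to the Day 1 column, states "All tests on Day 1 will be conducted predose".
- Footnote u, attached to the row for self-administration of investigational product, covers Days 1, 14 and 42 and states "All scheduled safety assessments will be conducted prior to dosing and all scheduled cognitive tests will be administered postdosing".
- Footnote a says "The scales are to be administered after the daily dose of IP during the Treatment Period". The Day 1 column sits under the Treatment Period heading.
- Protocol 8.4 says that at clinic visits "participants will self-administer the IP under staff supervision, followed by assessments of cognitive function".
- Protocol Section 10 says "These assessments are to be administered after the daily dose of IP during the Treatment Period".

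SAP Appendix A (Table 12) reprints footnotes a, b and u unchanged.

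The SAP's own intent is plain. Section 8.3.1.1 says "WAIS-IV Coding Test is collected at Baseline (Day -7), Day 1 (pre-dose), Day 14, Day 42 and Day 70", and Table 3 in Section 8.3.2 sets the baseline target as Day 1 predose, or failing that the latest available value before the first dose.

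SAP 8.1 then gives the operating rule. Where a test time exists, only an assessment before the first dose can serve as baseline. Otherwise "if the time of an assessment is not collected, the assessment on Day 1 is assumed to be prior to dosing", on the condition "if the protocol mentions that this assessment needs to be before dosing or it is collected as" predose.

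**The concern.** WAIS-IV Coding is a scheduled cognitive test on a day that footnote u names, so a site cannot obey both b and u. A site that doses first and tests afterwards is following written protocol text.

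The primary endpoint is change from this baseline to Day 42, and the baseline is also the covariate in the primary MMRM. If a score taken after the first dose is used and the drug acts within hours, part of the treatment effect is subtracted out as baseline in the SAGE-718 arm only. The SAP guards against this when the test time is known. When it is not, the SAP relies on what the protocol says about timing, and on Day 1 the protocol says two things.

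**Working it through.** **1. The timing instructions side by side, for Day 1 cognitive testing**

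| Place | Timing |
|---|---|
| Table 2 footnote b (and SAP Table 12) | before the dose |
| Table 2 footnote u (and SAP Table 12) | after the dose, Day 1 named |
| Table 2 footnote a | after the dose, general rule |
| Protocol 8.4 and Section 10 | after the dose, general rule |
| SAP 8.3.1.1 and Table 3 | before the dose |

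Footnote b could be read as a Day 1 exception to the general rules in footnote a, 8.4 and Section 10. It cannot be read that way against footnote u, which names Day 1.

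**2. A postdose Day 1 score traced through SAP 8.1**

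- Timed: the score is rejected and baseline becomes Day -7.
- Untimed but labelled predose: accepted on the label.
- Untimed and unlabelled: accepted, because footnote b satisfies the condition that the protocol calls for testing before dosing.

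In the third case one footnote certifies as predose a score that the other footnote told the site to collect postdose. For PVT and DSST, the note to SAP Table 2 foresees a Day 1 assessment taken after the first dose and states a replacement. WAIS-IV Coding has only the general 8.1 rule.

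**3. The plan's own sample size (SAP 5.2)**

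Inputs: effect size 0.75 (0.8/1.07 = 0.748), two-sided alpha 0.05, 80% power, 20% dropout. A two-sample t-test needs 28.9 per arm at 0.75 and 29.07 at 0.748, so 29 or 30 per arm. Power at 30 per arm and 0.75 is 81.5%. Dropout: 30/0.8 = 37.5, rounded up to 38 per arm, or 76. The stated figures reproduce and are not in dispute.

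**4. What contamination would do (illustration)**

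Three inputs are assumptions, not figures from the documents:

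- s: share of participants whose accepted baseline is an untimed postdose score
- f: fraction of the Day 42 effect already present at the Day 1 test
- b: slope of the Day 42 score on baseline

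With true effect D, the SAGE-718 mean baseline rises by s × f × D. The baseline-adjusted difference becomes D − b × s × f × D, so the retained fraction is 1 − b × s × f. Power is from the noncentral t with 58 degrees of freedom at d = 0.75 × (1 − b × s × f).

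| b | s | f | Retained | d | Power |
|---|---|---|---|---|---|
| any | any | 0 | 1.00 | 0.750 | 81.5% |
| 0.85 | 10% | 10% | 0.99 | 0.744 | 80.8% |
| 0.85 | 25% | 25% | 0.95 | 0.710 | 77.2% |
| 0.85 | 50% | 50% | 0.79 | 0.591 | 61.4% |
| 0.5 | 25% | 25% | 0.97 | 0.727 | 79.0% |
| 1.0 | 25% | 25% | 0.94 | 0.703 | 76.4% |

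Example: 1 − 0.85 × 0.25 × 0.25 = 0.947, and 0.75 × 0.947 = 0.710. A 4,000-run ANCOVA simulation with contaminated SAGE-718 baselines retained 0.99, 0.95 and 0.79 of the effect in the three b = 0.85 cases, matching the formula.

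**The case against.** The strongest reply is that the intent is settled. Footnote b sits on the Day 1 column and footnote u on the dosing row, Section 10 defers to Table 2, and the SAP says predose for Day 1 in two places. A postdose score that is known to be postdose already falls back to Day -7. Harm needs three things together: a site following u against b, no recorded time, and a cognitive effect soon after the first dose. Whether time is captured depends on the eCRF, which is not among the documents. The PVT and DSST note is also a weak precedent: it redefines a 7-day averaging window and says nothing about untimed scores.

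Much of this stands as a limit on size. The 50%/50% case is an extreme with no support in the documents, and at 10%/10% power hardly moves. The direction also rests on an acute benefit; an acute decrement would reverse it. The objection does not remove the contradiction. Clear intent in the SAP does not instruct sites, which work from the protocol, and the 8.1 default still accepts an untimed score on protocol wording alone.

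**Conclusion.** The concern holds and should be fixed. The conflict between footnotes b and u is certain, appears in both documents and affects the primary baseline. The route from that conflict to a contaminated baseline is conditional on untimed scores.

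The size of the bias cannot be derived, because the documents give neither test-time capture nor any acute effect. Under an acute benefit the bias is toward zero, so the cost is power and not false positives. The assumed cases in the table run from 80.8% to 61.4% against 81.5% uncontaminated. With no acute effect there is no attenuation.

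Timed postdose scores that fall back to Day -7 are a smaller matter. They carry one fewer prior test exposure, which randomization balances in expectation, so they mainly add noise.

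**What to change.** 1. Reconcile footnotes a, b and u, Protocol 8.4 and Section 10, and the SAP Appendix A copies, so that Day 1 cognitive testing has one timing that matches the SAP's predose baseline. Either take Day 1 out of the postdosing sentence or state the exception there. Footnote t, which places in-clinic mobile testing after dosing on dosing days, needs the same check.
2. Record the Day 1 WAIS-IV Coding test time or a predose flag, if the eCRF does not already do so.
3. Add a WAIS-IV Coding rule to the SAP: a Day 1 score is the baseline if its time precedes the first dose or it was collected as predose; otherwise use Day -7. Protocol wording alone should not establish predose status.
4. Report the number of participants by baseline source and arm.
5. If neither times nor labels were captured, keep the current default for the primary analysis and run a Day -7 baseline as a sensitivity analysis.

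The SAP side costs one sentence, one small table and possibly one extra model run, all feasible before database lock. The protocol side is a short text edit, but as an amendment it needs IRB re-approval (Protocol 15.1) for a study planned at about 30 sites. A new data field cannot repair tests already done. Without step 5, the rule in step 3 could move many baselines to Day -7 if nothing was captured.
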